### Treatment Period

Visit 1 for EP0151 will be the same as Visit 13 in EP0034 or SP848. Clinic visits are scheduled approximately every 26 weeks relative to the EP0151 Visit 1 date. Dose modifications required for optimization of seizure control or tolerability issues will be addressed in unscheduled visits or regularly scheduled visits. A visit window of  $\pm$ 7 days relative to Visit 1 is applicable for all regularly scheduled visits.

In EP0034 and SP848, study participants received flexible dosing based on the Investigator's clinical judgement, which ranged from a minimum dose of LCM 2mg/kg/day to a maximum dose of 12mg/kg/day or 600mg/day, whichever was lower. During EP0151 study visits, Investigators will be allowed to increase or decrease the dose of LCM to optimize tolerability and seizure control for each study participant. The Investigator may maintain the study participant's LCM dose, decrease the dose in decrements of 2mg/kg/day per week to a minimum dose of LCM 2mg/kg/day, or increase the dose in increments of 2mg/kg/day per week up to a maximum dose of LCM 12mg/kg/day or 600mg/day, whichever is lower. Lacosamide doses administered in this study must be from 2mg/kg/day to 12mg/kg/day. An IXRS will be used and should be called any time there is a dose increase or dose reduction (Figure 1-1).

### Early Termination Visit with tapering of LCM

Study participants who discontinue prematurely from EP0151 and who will not continue further treatment with LCM should gradually taper LCM. These study participants will perform an Early Termination Visit followed by the visits required for the End of Study Period. Study participants should be tapered off LCM at the recommended decrements (Table 6-2). The Taper Period is up to 4 weeks; a slower taper or faster taper is permitted, if medically necessary; however, the maximum duration of tapering should not exceed 6 weeks. All study participants who taper off LCM will attend a Final Visit 30 days after the final dose of LCM. In the case of LCM withdrawal and taper, the Investigator is allowed to add any other antiepileptic drugs (AEDs) during the End of Study Period, following the Investigator's medical judgment.

### Termination Visit

Study participants who remain in the Treatment Period and either reach 6 years of age or who participate in a region where marketing application approval is achieved for pediatric patients  $<4$  years of age and LCM oral solution is available (whichever is earliest) will have met the conditions for completing the study. A Termination Visit will be performed for these study participants at the time of the next scheduled visit. Study participants who reach the end of the study and choose to continue treatment with LCM may be immediately prescribed LCM. The Termination Visit will be the last study visit completed for study participants who continue treatment with prescribed LCM. Study participants who choose not to continue with LCM treatment and who are taking a dose of LCM 3mg/kg/day or higher will enter an End of Study Period following completion of the Termination Visit, and will gradually taper from LCM treatment during the Taper Period; a Final Visit will be conducted 30 days after the final dose of LCM.

In situations where provision of LCM oral solution in certain participants  $>6$  years of age (eg, developmental delay, need for more precise dosing as afforded by oral solution formulation, etc.) who may need a longer period of treatment with LCM oral solution, the situation will be

assessed for approval by UCB on a case-by-case basis following discussions with the participant's physician.

The maximum total duration of the study will be approximately 213 weeks, including an approximate 205-week Treatment Period and up to an 8 week End of Study Period (4-week Taper Period and 30-day Safety Follow-up Period). The end of the study is defined as the date of the last visit of the last study participant in the study.

#### **4.2 Scientific rationale for study design**

EP0151 is an open-label extension study designed to assess the long-term use of LCM (ranging in dose between LCM 2mg/kg/day to 12mg/kg/day) in pediatric study participants <6 years of age with epilepsy who have previously completed EP0034 or SP848.

EP0151 will allow study participants treated with LCM in EP0034 or SP848 to continue treatment with LCM until either the study participant reaches 6 years of age or until marketing application approval is achieved for pediatric patients <4 years of age in the region of participation and LCM oral solution is available (whichever is earliest). Cases where provision of LCM oral solution that do not meet these set criteria (eg, developmental delay, need for more precise dosing as afforded by LCM oral solution formulation, etc.) will be assessed on a case-by-case basis.

#### **4.3 Justification for dose**

Dose selection in EP0151 is based on the doses offered in the previous studies, EP0034 or SP848. During EP0151, Investigators will be allowed to increase or decrease the dose of LCM to optimize tolerability and seizure reduction for each study participant (Section 6.6). Lacosamide doses may be adjusted from a minimum dose of LCM 2mg/kg/day up to a maximum of 12mg/kg/day or 600mg/day, whichever is lower. This dose range is anticipated to be clinically safe and effective for monotherapy.

#### **4.4 End of study definition**

Study participants who remain in the Treatment Period and either reach 6 years of age or who participate in a region where marketing application approval is achieved for pediatric patients <4 years of age and LCM oral solution is available (whichever is earliest) will have met the conditions for completing the study.

The end of the study is defined as the date of the last visit of the last study participant in the study.

### **5 STUDY POPULATION**

Approximately 80 to 100 participants from SP848 and EP0034 may be eligible to enroll in this open label study.

Prospective approval of protocol deviations to recruitment and enrollment criteria, also known as protocol waivers or exemptions, is not permitted.

## **5.1 Inclusion criteria**

Participants are eligible to be included in the study only if all of the following criteria apply:

### **Age**

1. Participant is male or female, aged <6 years at the time of signing the Informed Consent Form (ICF).

### **Type of participant and disease characteristics**

2. Participant has completed participation in EP0034 or SP848.
3. Participant is expected to benefit from participation, in the opinion of the Investigator.

### **Informed consent**

4. An Independent Ethics Committee (IEC) approved written ICF is signed and dated by the participant or by the parent(s) or legal representative. The ICF or a specific Assent form, where required, will be signed and dated by minors (see Section 10.1.3).

## **5.2 Exclusion criteria**

Participants are excluded from the study if any of the following criteria apply:

### **Medical conditions**

1. Participant has any medical or psychiatric condition that, in the opinion of the Investigator, could jeopardize or would compromise the study participant's ability to participate in this study.
2. Participant has a known hypersensitivity to any components of the study medication or comparative drugs as stated in this protocol.

### **Prior/Concomitant therapy**

3. Participant is receiving any investigational drugs or using any experimental devices in addition to LCM.

### **Prior/Concurrent clinical study experience**

4. Participant meets a mandatory withdrawal criterion (ie, MUST withdraw criterion) for EP0034 or SP848, or is experiencing an ongoing serious AE (SAE).

### **Other exclusions**

5. Sensitivity to any of the study interventions, or components thereof, or drug or other allergy that, in the opinion of the Investigator or Medical Monitor, contraindicates participation in the study.

## **5.3 Lifestyle restrictions**

No restrictions are required.

## 5.4 Screen failures

Screen failures are defined as participants who consent to participate in the clinical study but are not subsequently entered in the study. A minimal set of screen failure information is required to ensure transparent reporting of screen failure participants to meet the Consolidated Standards of Reporting Trials publishing requirements and to respond to queries from regulatory authorities. Minimal information includes demography, screen failure details, eligibility criteria, and any SAE.

Individuals who do not meet the criteria for participation in this study (screen failure) may not be rescreened.

## 6 STUDY TREATMENTS

Study treatment is defined as any investigational treatment(s), marketed product(s), or placebo intended to be administered to a study participant according to the study protocol.

### 6.1 Treatments administered

A summary of treatments administered is provided in [Table 6-1](#).

**Table 6-1: Summary of treatments administered**

ARM Name	
Intervention name	Lacosamide
Type	Drug
Dose formulation	Oral solution
Unit dose strength(s)	LCM 10mg/mL
Dosage level(s)	Minimum dose of 2mg/kg/day to maximum dose of 12mg/kg/day or 600mg/day, whichever is lower, administered BID in the morning and evening.
Route of administration	Oral use
Use	Active open-label
IMP and NIMP	IMP
Sourcing	Provided by UCB
Packaging and labeling	Clinical drug supplies will be labeled in accordance with the current ICH guidelines on GCP and GMP and will include any locally required statements. If necessary, labels will be translated into the local language. Primary packaging: bottles with child-resistant closure
Current/former name(s) or alias(es)	Not applicable

BID=twice per day; GCP=Good Clinical Practice; GMP=Good Manufacturing Practice; ICH=International Council for Harmonisation; IMP=investigational medicinal product; LCM=lacosamide; NIMP=non-IMP

Study participants will receive LCM oral solution administered BID from a minimum dose of 2mg/kg/day to a maximum dose of 12mg/kg/day or 600mg/day, whichever is lower, based on optimization of seizure control and tolerability in the judgement of the Investigator.

The Investigator may maintain the LCM dose administered to the study participant in the previous study, decrease the dose to a minimum dose of LCM 2mg/kg/day, or increase the dose to a maximum dose of LCM 12mg/kg/day or 600mg/day, whichever is lower. An IXRS will be used and should be called any time there is a dose increase or dose reduction.

Study participants who are taking a dose of 3mg/kg/day or higher and who either withdraw during the study or complete the study and do not continue treatment with LCM should taper off LCM.

It is recommended that the dose be tapered gradually in weekly decrements according to [Table 6-2](#). A slower taper is permitted, if medically necessary, but should not exceed 6 weeks. In case of an emergency, a faster taper is permitted, after discussion with the Medical Monitor whenever possible.

**Table 6-2: Lacosamide doses for Taper Period**

LCM dose achieved	LCM doses for Taper Period			
	Week 1	Week 2	Week 3	Week 4
11-12mg/kg/day	9mg/kg/day	6mg/kg/day	4mg/kg/day	2mg/kg/day
9-10mg/kg/day	8mg/kg/day	6mg/kg/day	4mg/kg/day	2mg/kg/day
7-8mg/kg/day	6mg/kg/day	4mg/kg/day	2mg/kg/day	2mg/kg/day
5-6mg/kg/day	4mg/kg/day	2mg/kg/day	2mg/kg/day	----
3-4mg/kg/day	2mg/kg/day	2mg/kg/day	----	----

LCM=lacosamide

## **6.2 Preparation, handling, storage, and accountability requirements**

The Investigator (or designee) must confirm appropriate temperature conditions have been maintained during transit for all study treatment received and any discrepancies are reported and resolved before use of the study treatment.

Only participants enrolled in the study may receive study treatment and only authorized site staff may supply or administer study treatment. All study treatments must be stored in a secure, environmentally controlled, and monitored (manual or automated) area in accordance with the labeled storage conditions, with access limited to the Investigator and authorized site staff.

The Investigator, institution, or the head of the medical institution (where applicable) is responsible for study treatment accountability, reconciliation, and record maintenance (ie, receipt, reconciliation, and final disposition records).

In case an out-of-range temperature is noted, it must be immediately reported as per instructions contained in the investigational medicinal product (IMP) Handling Manual.

The Investigator (or designee) will instruct the participant to store the study medication following the instructions on the label.

Further guidance and information for the final disposition of unused study treatment are provided in the IMP Handling Manual.

### **6.2.1 Drug accountability**

The Drug Accountability form will be used to record study medication dispensing and return information on a by-participant basis and will serve as source documentation during the course of the study. Details of any study medication lost, damaged (due to breakage or wastage), not used, partially used, disposed of at the study site, or returned to the Sponsor or designee must also be recorded on the appropriate forms. All supplies and pharmacy documentation must be made available throughout the study for UCB (or designee) to review.

The Investigator (or designee) is responsible for retaining all used, unused, and partially used containers of study medication until returned or destroyed.

The Investigator may assign some of the Investigator's duties for drug accountability at the study site to an appropriate pharmacist/designee.

The Investigator must ensure that the study medication is used only in accordance with this protocol.

Periodically, and/or after completion of the clinical phase of the study, all used (including empty containers), partially used, unused, damaged, and/or expired study medication must be reconciled and either destroyed at the site according to local laws, regulations, and UCB standard operating procedures or returned to UCB (or designee). Investigational medicinal product intended for the study cannot be used for any other purpose than that described in this protocol.

### **6.3 Measures to minimize bias: randomization and blinding**

This is an open-label study. Therefore, randomization is not applicable and no blinding is required.

Study participant numbers that were utilized in SP848 and EP0034 will continue to be used in EP0151. The study participant number must be incorporated into the electronic Case Report Form (eCRF).

The IXRS will generate individual assignments for kits of study medication, as appropriate, according to the visit schedule and assigned dose. Participant numbers and kit numbers will be tracked via the IXRS. The IXRS will allocate kit numbers to the participant based on the participant number during the course of the study.

The participant number will be required in all communication between the Investigator or designee and the IXRS regarding a particular participant.

### **6.4 Treatment compliance**

At each visit after study medication is dispensed, participants must return all unused study medication and empty study medication containers. Drug accountability must be done in the participant's presence in order to obtain explanations regarding discrepancies in compliance with the dosing regimen. Drug accountability must be recorded on the Drug Accountability form.

If a participant is found to be persistently noncompliant (defined as less than 75% or more than 125% compliant with the dosage schedule), the Sponsor, in conjunction with the Investigator, will make a decision as to whether the participant should be withdrawn from the study.

## **6.5 Concomitant medication(s)/treatment(s)**

### **6.5.1 Permitted concomitant treatments (medications and therapies)**

The following concomitant medications are permitted during the study:

- If needed to optimize tolerability and seizure reduction in selected participants, concomitant AEDs may be carefully tapered and discontinued to achieve LCM monotherapy. New concomitant AEDs may be introduced as treatment if the medication has been approved by the regulatory authorities in the country in which the participant lives. New concomitant AEDs should be added only when the participant has not optimally or adequately responded to a maximum tolerated dose of LCM.
- Implantation of and/or changes in vagal nerve stimulation settings are permitted.
- The Investigator must contact the Medical Monitor if surgery is planned for any participant. In general, it is not necessary to discontinue LCM for participants undergoing surgery, although each case must be discussed on a case-by-case basis. The Investigator must contact the Medical Monitor before re-starting LCM after a surgery.

### **6.5.2 Prohibited concomitant treatments (medications and therapies)**

The following concomitant medications are prohibited during the study:

- Clozapine
- Monoamine oxidase-A inhibitors
- Cannabidiols (when not approved or indicated for epilepsy by local health authority)

### **6.5.3 Rescue medication**

Therapy that becomes necessary, in the Investigator's opinion, during the course of the study must not be refused to a participant, even if described above as a therapy that is expressly not permitted in the frame of this study. The study participant's participation in this study may be discontinued in such a case.

Any rescue medication is allowed. The date and time of rescue medication administration, as well as the name and dosage regimen of the rescue medication, must be recorded in the eCRF.

## **6.6 Dose modification**

In case a dose modification is necessary, the study treatment will be administered as described in Section 6.1. The IXRS should be called any time there is a dose increase or dose reduction.

## **6.7 Criteria for study hold or dosing stoppage**

Selected data, including SAEs and AEs, from this study will be reviewed periodically to detect as early as possible any safety concern(s) related to the study medication and will make recommendations on the continuation or modification of the study as appropriate.

## 6.8 Treatment after the end of the study

There is no treatment planned after the end of the study.

Study participants who reach the end of the study and choose to continue treatment with LCM may be immediately prescribed LCM following the Termination Visit.

## 7 DISCONTINUATION OF STUDY MEDICATION AND PARTICIPANT DISCONTINUATION/WITHDRAWAL

[figure not shown]
### 7.1 Discontinuation of study medication

#### 7.1.1 Liver chemistry stopping criteria

Discontinuation of study treatment for abnormal liver function should be considered by the Investigator when a participant meets one of the conditions outlined in [Figure 7-1](#) or [Figure 7-2](#) or if the Investigator believes that it is in best interest of the participant.

Study medication will be discontinued immediately and permanently for a study participant if liver chemistry stopping criteria are met.

[figure not shown]
**Figure 7-1: Liver chemistry stopping criteria and increased monitoring algorithm**

ALT=alanine aminotransferase; AST=aspartate aminotransferase; INR=international normalized ratio; SAE=serious adverse event; ULN=upper limit of normal

Note: Algorithm for continued therapy with increased liver chemistry monitoring can be found in [Figure 7-2](#).

**Figure 7-2: Liver chemistry increased monitoring algorithm with continued study intervention for participants with ALT  $\geq 3$ xULN but  $< 8$ xULN**

ALT=alanine aminotransferase; AST= aspartate aminotransferase; bili=bilirubin; INR=international normalized ratio; SAE=serious adverse event; ULN=upper limit of normal

Specific assessments and follow-up actions for potential drug-induced liver injury are provided in Appendix 6 (Section 10.6).

Study participants with potential drug-induced liver injury (PDILI) must be assessed to determine if study medication must be immediately and permanently discontinued. In addition, all concomitant medications and herbal supplements that are not medically necessary should also be discontinued.

The PDILI criteria below require immediate and permanent discontinuation of study medication:

- Participants with either of the following:
  - Alanine aminotransferase (ALT) or aspartate aminotransferase (AST)  $\geq 5$ x upper limit of normal (ULN)
  - ALT or AST  $\geq 3$ xULN and coexisting total bilirubin  $\geq 2$ xULN

The PDILI criterion below requires immediate discontinuation of study medication:

- Participants with ALT or AST  $\geq 3$ xULN who exhibit temporally associated symptoms of hepatitis or hypersensitivity. Hepatitis symptoms include fatigue, nausea, vomiting, right

upper quadrant pain or tenderness. Hypersensitivity symptoms include fever (without clear alternative cause), rash, or eosinophilia (ie, >5%).

The PDILI criterion below allows for participants to continue on study medication at the discretion of the Investigator:

- Participants with ALT or AST  $\geq 3 \times \text{ULN}$  (and  $\geq 2 \times \text{Baseline}$ ), and  $< 5 \times \text{ULN}$ , total bilirubin  $< 2 \times \text{ULN}$ , and no eosinophilia (ie,  $\leq 5\%$ ), with no fever, rash, or symptoms of hepatitis (eg, fatigue, nausea, vomiting, right upper quadrant pain or tenderness).

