**Table 10-1: Phase 3-4 liver chemistry stopping criteria and follow-up assessments**

Liver Chemistry Stopping Criteria	
ALT-absolute	ALT≥8xULN
ALT increase	ALT≥5xULN but <8xULN persists for ≥2 weeks ALT≥3xULN but <5xULN persists for ≥4 weeks
Bilirubina,b	ALT≥3xULN and bilirubin ≥2xULN (>35% direct bilirubin)
INRb	ALT≥3xULN and INR>1.5, if INR measured
Cannot monitor	ALT≥5xULN but <8xULN and cannot be monitored weekly for ≥2 weeks ALT≥3xULN but <5xULN and cannot be monitored weekly for ≥4 weeks
Symptomatic	ALT≥3xULN associated with symptoms (new or worsening) believed to be related to liver injury or hypersensitivity
Suggested Actions and Follow up Assessments	
Actions	

• Immediately discontinue study medication

• Report the event to UCB within 24 hours

• Complete the Liver Event eCRF, and complete an SAE data collection tool if the event also met the criteria for an SAEb

	
Follow-up Assessments	

• Viral hepatitis serologyd

• Obtain INR and recheck with each liver chemistry assessment until the transaminases values show downward trend

	

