**Table 10-1: Phase 3-4 liver chemistry stopping criteria and follow-up assessments**

Liver Chemistry Stopping Criteria	

 
• Perform liver chemistry follow-up assessments
 
• Monitor the participant until liver chemistry test abnormalities resolve, stabilize, or return to baseline (see MONITORING)
 
• Do not restart/rechallenge participant with study medication unless allowed per protocol and UCB approval is granted
 
• If restart/rechallenge not allowed per protocol or not granted, permanently discontinue study medication and continue participant in the study for any protocol specified follow up assessmentsConsider the need for a toxicology screening
 
 
MONITORING:
 
For bilirubin or INR criteria
 
 
• Repeat liver chemistry tests (include ALT, AST, alkaline phosphatase, bilirubin) and perform liver event follow-up assessments within 24 hours
 
• Monitor participant twice weekly until liver chemistry test abnormalities resolve, stabilize, or return to baseline
 
• A specialist or hepatology consultation is recommended
 
 
For all other criteria
 
 
• Repeat liver chemistry tests (include ALT, AST, alkaline phosphatase, bilirubin) and perform liver chemistry follow-up assessments within 24 to 72 hours
 
• Monitor participants weekly until liver chemistry abnormalities resolve, stabilize, or return to baseline
 
	
 
• Only in those with underlying chronic hepatitis B at study entry (identified by positive hepatitis B surface antigen), quantitative hepatitis B DNA and hepatitis delta antibodyc
 
• Obtain blood sample for PK analysisa
 
• Serum CPK and LDH
 
• Fractionate bilirubin, if total bilirubin <math>\geq 2 \times \text{ULN}</math>
 
• Obtain complete blood count with differential to assess eosinophilia
 
• Record the appearance or worsening of clinical symptoms of liver injury (eg, fatigue, nausea, vomiting, right upper quadrant pain), or hypersensitivity, on the AE report form
 
• Record use of concomitant medications (including acetaminophen, herbal remedies, and other over-the-counter medications) on the Concomitant Medications eCRF.
 
 
For bilirubin or INR criteria:
 
Anti-nuclear antibody, anti-smooth muscle antibody, Type 1 anti-liver kidney microsomal antibodies, and quantitative total IgG or gamma globulins
 
 
• Serum acetaminophen adduct HPLC assay (quantifies potential acetaminophen contribution to liver injury in participants with definite or likely acetaminophen use in the preceding week [James, 2009])
 
 
NOTE: Not required in China.
 
 
• Liver imaging (ultrasound, magnetic resonance, or computerized tomography) and/or liver biopsy to evaluate liver disease; complete Liver Imaging and/or Liver Biopsy eCRFs
 

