
AE=adverse event; ALT=alanine aminotransferase; AST=aspartate aminotransferase; CPK=creatine phosphokinase; DNA=deoxyribonucleic acid; eCRF=electronic Case Report Form; HBcAb=hepatitis B core antibody; HBsAg=hepatitis B surface antigen; HPLC=high performance liquid chromatography; IgG=immunoglobulin G; IgM= immunoglobulin M; INR=internal normalized ratio; LDH=lactate dehydrogenase; PCR=polymerase chain reaction; PK=pharmacokinetic; RNA=ribonucleic acid; ULN=upper limit of normal; SAE=serious adverse event

a Serum bilirubin fractionation should be performed if testing is available. If serum bilirubin fractionation is not immediately available, discontinue study medication if ALT  $\geq 3 \times \text{ULN}$  and bilirubin  $\geq 2 \times \text{ULN}$ . Additionally, if

serum bilirubin fractionation testing is unavailable, **record the absence/presence of detectable urinary bilirubin on dipstick** which is indicative of direct bilirubin elevations suggesting liver injury.

b All events of ALT $\geq$ 3xULN and bilirubin $\geq$ 2xULN (>35% direct bilirubin) or ALT $\geq$ 3xULN and INR $>$ 1.5 may indicate severe liver injury (**possible ‘Hy’s Law’**) and **must be reported as an SAE (excluding studies of hepatic impairment or cirrhosis)**. The INR measurement is not required and the stated threshold value will not apply to participants receiving anticoagulants.

c New or worsening symptoms believed to be related to liver injury (such as fatigue, nausea, vomiting, right upper quadrant pain or tenderness, or jaundice) or hypersensitivity (such as fever, rash or eosinophilia).

d Includes: Hepatitis A IgM antibody; HBsAg and HBCAb; hepatitis C RNA; cytomegalovirus IgM antibody; Epstein-Barr viral capsid antigen IgM antibody (or if unavailable, heterophile antibody or monospot testing); and hepatitis E IgM antibody.

e If hepatitis delta antibody assay cannot be performed, it can be replaced with a PCR of hepatitis D RNA virus (where needed) (Le Gal, 2005).

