**Table 10-2: Phase 3-4 liver chemistry increased monitoring criteria with continued study medication**

Liver Chemistry Increased Monitoring Criteria	
Criteria	Actions
ALT $\geq$ 5xULN and <8xULN and bilirubin <2xULN without symptoms believed to be related to liver injury or hypersensitivity, and can be monitored weekly for 2 weeks  OR  ALT $\geq$ 3xULN and <5xULN and bilirubin <2xULN without symptoms believed to be related to liver injury or hypersensitivity, and can be monitored weekly for 4 weeks	

Notify the UCB Medical Monitor within 24 hours of learning of the abnormality to discuss study participant safety

Participant can continue study medication

Participant must return weekly for repeat liver chemistry tests (ALT, AST, alkaline phosphatase, bilirubin) until the abnormalities resolve, stabilize, or return to baseline

If at any time, the participant meets liver chemistry stopping criteria, proceed as described in Table 10-1

If ALT decreases from ALT<math>\geq</math>5xULN and <8xULN to <math>\geq</math>3xULN but <5xULN, continue to monitor liver chemistries weekly

If, after 4 weeks of monitoring, ALT <3xULN and bilirubin <2xULN, monitor participants twice monthly until liver chemistry tests resolve, stabilize, or return to baseline

ALT=alanine aminotransferase; AST=aspartate aminotransferase; ULN=upper limit of normal

---

**10.7      Appendix 7: Medical device adverse events, adverse device effects, serious adverse events and device deficiencies: definition and procedures for recording, evaluating, follow-up, and reporting**

Not applicable.

This document cannot be used to support any marketing authorization application and any extensions or variations thereof.

PUBLIC COPY

---

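### Section 7.1.1 orders a permanent stop at ALT or AST ≥5xULN, Tables 10-1 and 10-2 let dosing continue at ALT 5 to <8xULN, and no text shown says which rule prevails

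*Protocol*

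**What the plan says.** **Section 7.1.1 (text after Figures 7-1 and 7-2).** Two findings are listed under the statement "The PDILI criteria below require immediate and permanent discontinuation of study medication": ALT or AST ≥5xULN, and ALT or AST ≥3xULN together with total bilirubin ≥2xULN. The first carries no condition on bilirubin, symptoms or duration. Investigator discretion to continue is limited to ≥3 and <5xULN, with bilirubin <2xULN and no symptoms or eosinophilia.

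**Title of Figure 7-2 (inside Section 7.1.1).** It describes continued treatment with increased monitoring for ALT ≥3 but <8xULN.

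**Table 10-1 (Appendix 6).** The absolute ALT stop is at ≥8xULN. Below that, the stops include:
- "ALT≥5xULN but <8xULN persists for ≥2 weeks"
- "ALT≥3xULN but <5xULN persists for ≥4 weeks"
- either band, when weekly monitoring is not possible
- "ALT≥3xULN and bilirubin ≥2xULN (>35% direct bilirubin")
- "ALT≥3xULN and INR>1.5, if INR measured"
- ALT ≥3xULN with symptoms of liver injury or hypersensitivity.

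**Table 10-2 (Appendix 6).** For ALT ≥5 and <8xULN, bilirubin <2xULN, no such symptoms and weekly monitoring feasible for 2 weeks, the action is "Participant can continue study medication".

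**Links between them.** Section 7.1.1 sends the reader to Appendix 6 for assessments and follow-up. The footnote to the laboratory table in Appendix 2 cites Sections 7.1.1 and 10.6 together.

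**The concern.** The same laboratory result in a child under 6 means a permanent stop on one page and permitted dosing on another. The rule is mandatory and the site is the first to apply it: from Visit 2 blood is analysed locally and individual values are not entered in the eCRF (Section 8.2.3), and no Data Monitoring Committee is planned (Section 9.6). A site acting in good faith on Table 10-2 would commit a deviation from a safety stopping rule. Two sites could also handle identical children differently.

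**Working it through.** No arithmetic applies, so the rules are set side by side. Hold the following fixed: bilirubin <2xULN, no symptoms, no eosinophilia, weekly monitoring feasible, and INR not measured or ≤1.5. Take the ≥2xBaseline clause in the Section 7.1.1 discretion criterion as met.

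| ALT | Section 7.1.1 prose | Tables 10-1 and 10-2 | Result |
|---|---|---|---|
| 3 to <5xULN, under 4 weeks | may continue, Investigator's discretion | can continue | agree |
| 3 to <5xULN, 4 weeks or more | may continue, no time limit | stop | prose looser |
| 5 to <8xULN, under 2 weeks | immediate, permanent stop | can continue | **conflict** |
| 5 to <8xULN, 2 weeks or more | immediate, permanent stop | stop | agree on stopping |
| ≥8xULN | immediate, permanent stop | stop | agree on stopping |

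**One case through both rules.** Take a newly raised ALT of 6xULN with bilirubin 1xULN.
- Section 7.1.1: 6 ≥ 5, so stop permanently.
- Table 10-1: 6 < 8, not yet two weeks, monitorable, no symptoms and no bilirubin or INR trigger, so no stopping criterion is met.
- Table 10-2: 5 ≤ 6 < 8 and 1 < 2, so the child can continue.

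**Is there a precedence rule?**
- The cross-references in Section 7.1.1 and Appendix 2 point to both places without ranking them.
- Appendix 6 asks for an agreed monitoring plan when ALT exceeds 5xULN and does not mention the Section 7.1.1 stop.
- Section 8 asks for immediate safety concerns to be discussed with the Sponsor. It does not choose between the rules, and it bars waivers.
- Amendment 1 only added an EU trial number, so neither text is superseded.

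**Secondary misalignments.** These are limited to the Section 7.1.1 prose, because the bodies of the figures are not shown.
- *Analyte.* The prose uses ALT or AST; the tables set thresholds for ALT only. Isolated AST of 6xULN is a mandatory stop in the prose and has no criterion in the tables.
- *Bilirubin.* The prose uses total bilirubin; Table 10-1 adds a direct fraction above 35%. Footnote a relaxes this only when the fraction cannot be had promptly: "If serum bilirubin fractionation is not immediately available, discontinue study medication if ALT" is ≥3xULN and bilirubin ≥2xULN. With ALT 4xULN, bilirubin 2.5xULN, a measured direct fraction ≤35% and no other trigger, the prose stops. Table 10-1 does not stop, and Table 10-2 does not apply because it needs bilirubin <2xULN.
- *Extra stops at 3 to <5xULN.* Table 10-1 adds four weeks' persistence, inability to monitor weekly, and INR >1.5 if measured. The prose has none of these.

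**The case against.** The strongest reply is that the conflict is one of permission against obligation. Table 10-2 allows continuation but does not require it, so stopping always complies with both. The title of Appendix 6 calls its actions suggested, and Section 7.1.1 refers to it only for assessments and follow-up, which favours Section 7.1.1. A site is also not alone: Table 10-2 requires contact with the Medical Monitor within 24 hours, and Appendix 6 requires a plan agreed with the Study Physician.

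The point about a compliant action stands and limits the harm. The rest does not settle the matter. Table 10-1 is itself headed as stopping criteria, Appendix 2 calls the actions required, and the Figure 7-2 title places the 8xULN version inside Section 7.1.1. Consultation helps only if those consulted know which rule applies.

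Several stronger readings are tempting but not supported:
- *The stricter rule at 3 to <5xULN exists only in the appendix.* This cannot be verified. Section 7.1.1 makes Figures 7-1 and 7-2 part of the rule, both abbreviation lists include INR, and the figures may carry these stops.
- *The AST and bilirubin differences are further contradictions.* They are alignment gaps: the tables lack a criterion, and Section 7.1.1 still gives a clear stop.
- *Table 10-1 reopens dosing after a permanent stop.* It bars restart "unless allowed per protocol and UCB approval is granted" and otherwise defaults to permanent discontinuation. No liver text shown allows a restart.
- *The general instruction to taper in Section 7.2 defeats an immediate stop.* That is a separate question, partly met by the faster tapers allowed in Sections 4.1 and 6.1.

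**Conclusion.** The contradiction is real and should be corrected. It is confined to ALT ≥5 and <8xULN, bilirubin <2xULN, no symptoms, feasible weekly monitoring, no INR trigger and less than two weeks' duration. There, following Table 10-2 breaches Section 7.1.1, while stopping breaches neither.

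The conclusion rests on the text and figure titles as shown. A body of Figure 7-2 that matched its title would not remove the conflict with the Section 7.1.1 bullets.

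The size cannot be put as a number of children, because the documents give no frequency of ALT rises. A reader might count the combinations of laboratory values on which the rules differ, but such a count depends on the values chosen and measures no risk. A reader might also infer an effect on the withdrawal endpoints; none can be derived. Nor do the documents show whether 5xULN or 8xULN was intended. The error is that both stand.

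**What to change.** State one liver stopping rule set and align the Section 7.1.1 text, Figures 7-1 and 7-2, and Tables 10-1 and 10-2 to it. The alignment should cover the analyte (ALT or AST) and whether the bilirubin stop needs a direct fraction.

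Until the amendment is in force, tell sites by memo that:
- the mandatory stop at ALT or AST ≥5xULN in Section 7.1.1 governs over the continuation branch of Table 10-2
- any Table 10-1 stop at ALT 3 to <5xULN also applies.

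If the sponsor's hepatic-safety experts intend the 8xULN set, amend the Section 7.1.1 bullets instead and give the reason.

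The cost is amendment wording and a site memo, with no added participants or scheduled procedures. The small downside of the interim default is that some children with a transient rise to 5 to <8xULN will stop lacosamide when Table 10-2 would have let them continue.
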